8.3 Procedures for Final Study Entry

The results from the screening ocular and physical examinations, and laboratory tests (hematology/blood chemistry/urinalysis) must be evaluated and determined to be acceptable to the investigator prior to the patient's entry into the study. If repeat laboratory tests are done, the results must be reviewed prior to study treatment initiation on Day 1. Reading Center qualification of endothelial cell density must be confirmed by the Baseline visit. After confirmation of eligibility on Day 1, IV/WRS is contacted for randomization. However, this contact for randomization may take place at the end of the Baseline visit if needed. See Section 5.5 for the method for assignment to treatment groups/randomization.

A patient is considered to have enrolled in the study at the time of the first study treatment administration (or Sham).

[REDACTED]

[REDACTED]

[REDACTED]

[REDACTED]

[REDACTED]

Approval Date: 16-Mar-2017

[Redacted text block containing multiple paragraphs of obscured content]

[figure not shown]
[Redacted text line]

[Redacted text line]

[figure not shown]
[Redacted text line]

[figure not shown]
[Redacted text block containing two lines of obscured content]

Approval Date: 16-Mar-2017

[figure not shown]

Approval Date: 16-Mar-2017

[figure not shown]

[figure not shown]
Approval Date: 16-Mar-2017

[figure not shown]
Approval Date: 16-Mar-2017

[figure not shown]
Approval Date: 16-Mar-2017

[figure not shown]
Approval Date: 16-Mar-2017

[figure not shown]
Approval Date: 16-Mar-2017

[figure not shown]
Approval Date: 16-Mar-2017

[figure not shown]
Approval Date: 16-Mar-2017

[figure not shown]
Approval Date: 16-Mar-2017

[figure not shown]
Approval Date: 16-Mar-2017

[figure not shown]
Approval Date: 16-Mar-2017

[figure not shown]
Approval Date: 16-Mar-2017

[figure not shown]
Approval Date: 16-Mar-2017

[figure not shown]
Approval Date: 16-Mar-2017

Approval Date: 16-Mar-2017

Approval Date: 16-Mar-2017

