5.3 Methods for Masking

Patients in the Control group will receive timolol eye drops BID plus Sham administration in both eyes. Vehicle eye drops will be used BID to mask the treatment of patients receiving Bimatoprost SR in the study eye. Treatment for fellow eyes of patients assigned to 1 of the 2 Bimatoprost SR dose groups will be a Sham administration procedure + timolol eye drops BID.

The site coordinator and designated staff will not be masked to whether the patient received 1 of the 2 dose strengths of Bimatoprost SR or the Sham administration procedure, but will be masked to the specific implant dose strength. The patient and the remaining staff will be masked to the patient's treatment assignment. Efficacy IOP measurements will be masked by

using a 2-person reading method as described in Section 6.1.1 (for optional postoperative IOP measurements for patients with sickle cell disease or trait [or other hemoglobinopathies], see Section 8.4).

The site staff who perform IOP readings will be masked regarding the study eye (which eye received Bimatoprost SR or the Sham administration procedure), Bimatoprost SR dose strength, and the study treatments that are delivered in bottles. Site personnel and patients will be instructed and reminded throughout the study not to discuss study medication assignments to ensure maintenance of the masking.

Designated site personnel will be responsible for receiving, dispensing, and collecting study medication and performing drug accountability, as well as verification of patient dosing compliance; sites are encouraged to assign an unmasked staff member (eg, site coordinator) to this task to avoid unmasking additional personnel. Based on the randomization schedule, these designated personnel will dispense the study medication to the patient. All bottles will contain similar masked labels for the study, identifying the eye of administration by “Right” and “Left”.

In the event that the patient requires topical corticosteroids or anti-inflammatory drops in only one eye during the 7 days after the administration procedure, in order to maintain masking the investigator will be instructed to dispense the required medication without disclosing which eye is the study eye, or the etiology of the signs/symptoms that require the medication.

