5.5 Method for Assignment to Treatment Groups/Randomization

Prior to initiation of any study procedures, each patient who provides informed consent will be assigned a subject number that will serve as the patient's identification number on all study documents.

Eligible patients will be randomly assigned to 1 of 3 treatment groups in a 1:1:1 ratio to receive study Bimatoprost SR 10 µg, Bimatoprost SR 15 µg, or timolol. The randomization will be stratified by Baseline Hour 0 IOP (baseline study eye IOP ≤ 25 mm Hg or > 25 mm Hg).

For determination of stratification group assignment for each patient, sites will be required to enter baseline IOP at Hour 0 data into electronic data capture (EDC). Electronic data capture will assign a stratification code associated with one of the stratification groups for the Baseline Hour 0 IOP.

At the time of randomization (Cycle 1 Day 1 Administration Day) an automated Interactive Voice/Web Response System (IV/WRS) will be used to manage the randomization and treatment assignment based on a randomization scheme prepared by Allergan Biostatistics. The site will enter the stratification group assignment code (obtained from the EDC) into IV/WRS at the time of randomization. A randomization number will be assigned to a patient according to the order of enrollment within each IOP stratum (baseline study eye Hour 0 IOP ≤ 25 mm Hg or > 25 mm Hg) across the study. That is, IV/WRS will assign the next available randomization number to the patient at the time when the investigator requests randomization. Study medication will be labeled with medication kit numbers. The IV/WRS system will provide the site with the specific medication kit number(s) for each randomized patient at the time of randomization. Sites will dispense study medication according to the

IV/WRS instructions. Sites will also call the IVRS or log onto the IWRS at subsequent visits to obtain a study medication kit number for dispensing study medication. Sites will receive the IV/WRS confirmation notifications for each transaction. All notifications are to be maintained with the study source documents.

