6.0 PATIENT POPULATIONS

6.1 INTENT-TO-TREAT POPULATION

The intent-to-treat (ITT) population will consist of all randomized patients.

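### Protocol Sections 5.5 and 8.3 disagree on when patients are randomised, and the exception in 8.3 means that allocation could precede the final eligibility decision

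*Protocol*

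**What the plan says.** Protocol Section 5.5 ties randomisation to Day 1: "At the time of randomization (Cycle 1 Day 1 Administration Day) an automated Interactive Voice/Web Response System (IV/WRS) will be used". It offers no Baseline option. On what the site then receives, it says: "The IV/WRS system will provide the site with the specific medication kit number(s) for each randomized patient at the time of randomization".

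Protocol Section 8.3 starts from the same position: "After confirmation of eligibility on Day 1, IV/WRS is contacted for randomization". The next sentence opens an exception: "However, this contact for randomization may take place at the end of the Baseline visit if needed". Just before these, the same paragraph says of laboratory work: "If repeat laboratory tests are done, the results must be reviewed prior to study treatment initiation on Day 1". Section 8.3 then dates enrolment from the first administration, which comes after randomisation.

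On masking, Protocol Section 5.3 states: "The site coordinator and designated staff will not be masked to whether the patient received 1 of the 2 dose strengths of Bimatoprost SR". That sentence goes on to name Sham as the alternative, and it keeps these staff masked only to the dose strength. Patients and the remaining staff are masked to treatment.

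SAP Section 6.1 defines the main analysis set: "The intent-to-treat (ITT) population will consist of all randomized patients".

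**The concern.** Two current sections give sites different instructions on when to randomise, and the looser one reverses the usual order for some patients. Concealment of the allocation should last until the decision to admit the patient is final. If the assignment exists while an entry check is still open, someone who knows that a real intracameral injection is due, rather than a needleless touch, could weigh a borderline finding differently. Losses between Baseline and Day 1 could then differ by arm.

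The primary analysis would not repair this. A patient dropped before administration counts as randomised and so belongs to the ITT population, but has no Week 2, 6 or 12 IOP for the model to use.

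**Working it through.** **Step 1. The order of events, section by section.**

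| Event | Protocol 5.5 | Protocol 8.3, main rule | Protocol 8.3, exception |
|---|---|---|---|
| IV/WRS contact | Day 1 Administration Day | Day 1, after eligibility is confirmed | End of the Baseline visit |
| Kit numbers issued | At randomisation | Hence Day 1 | Hence Baseline |
| Eligibility final | Before randomisation (eligible patients are randomised) | Before contact | Not stated |

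The first two columns agree. The third conflicts with both.

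**Step 2. Can an entry check still be open after Baseline?** Yes. Section 8.3 lets repeat laboratory results be reviewed up to treatment on Day 1. It asks for acceptable screening results before the patient's entry into the study, but does not tie entry to randomisation, and it dates enrolment from first administration. Endothelial cell density is different: it must be qualified by the Baseline visit. Exclusion 14 in Section 4.4 also runs to Day 1, but recent eye surgery is a matter of fact and leaves little room for judgement.

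**Step 3. Who could know the arm?** Section 5.3 leaves the coordinator and designated staff unmasked to implant versus Sham. Section 5.9.4, on the optional pressure check after administration, words the investigator together with other unmasked personnel, so the investigator may be unmasked too. No visible text says that the kit number, the carton or IV/WRS shows the arm at the moment of randomisation.

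**Step 4. What happens to a dropped patient in the analysis?**
- ITT population (SAP 6.1): included.
- Primary MMRM (SAP 10.1.1): the responses are IOP changes at Weeks 2, 6 and 12. With none observed, the patient contributes nothing.
- Safety population (SAP 6.2): excluded if no study treatment was received.
- Per-protocol population (SAP 6.3): excluded, because the primary variable was not measured.
- Multiple imputation (SAP 10.1.1): can include the patient, but as a sensitivity analysis that imputes within treatment group from patients with data.

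**Step 5. Power.** The plan's own figures were reproduced first. Inputs from Protocol Section 7.7 are SD 4.0 mm Hg, within-subject correlation 0.6 and 180 per group. The 10 µg minus timolol difference is -0.25 mm Hg at Weeks 2 and 6 and 0 at Week 12. The 15 µg arm is 0.25 mm Hg better throughout, so -0.50 and -0.25.

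At each timepoint the upper limit is the observed difference + t(0.975, 2n - 2) × √((s₁² + s₂²)/n). The standard error at planning values is 4.0 × √(2/180) = 0.42 mm Hg. A dose passes if the upper limit is ≤ 1.5 at all 6 timepoints and ≤ 1.0 at 3 or more.

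With 20,000 simulated trials, power is 95.1% for 15 µg (stated 95%). For 10 µg it is 80.7% when 15 µg must pass first (stated 81%), or 83.2% without that condition. Enrolment is 180/(1 - 0.10) = 200 per group, as stated.

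The documents do not say how many patients might be randomised at Baseline and then not treated. As an assumption only, a further loss of 2%, 5% or 10% in every group gives (8,000 trials each):

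| Further loss | n per group | Power, 15 µg | Power, 10 µg (15 µg first) |
|---|---|---|---|
| 2% | 180 × 0.98 ≈ 176 | 94.3% | 79.6% |
| 5% | 180 × 0.95 = 171 | 94.0% | 77.7% |
| 10% | 180 × 0.90 = 162 | 92.2% | 75.0% |

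Even this may overstate the effect. If the 600 to be enrolled are counted as Section 8.3 defines enrolment, patients lost before administration fall outside the 600.

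**The case against.** The strongest reply is that only the wording is at fault. Section 5.5 and SAP Section 4.0 both say that patients who meet the criteria are the ones randomised. The early contact can be read as moving together with the confirmation of eligibility. Section 8.4, with the visit procedures, is redacted and may hold a safeguard. The only visible Baseline window, in the Amendment 2 summary, suggests at most 3 days before Day 1. Applicators are sealed in foil pouches in their own cartons (Section 10.5.1), with the study and kit numbers named as the label identifiers, so early knowledge of the arm is not shown.

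Much of this stands. It limits the concern to a possibility, but does not remove the conflict between 5.5 and 8.3. Nothing visible says that confirmation moves with the contact, and the laboratory sentence shows that a check may outlast Baseline.

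It is also true that SAP Section 7.0 already tabulates ITT and Safety counts by treatment group, and discontinuation reasons by group for ITT. The number untreated can therefore largely be inferred, although no such category is named. A patient randomised on Day 1 but not treated would also lack post-baseline IOP; moving randomisation to Day 1 shortens the interval but does not abolish it.

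A reader might infer that patients would be more reluctant to go ahead when a real injection is due. The documents do not support this: patients are masked to their arm.

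**Conclusion.** The conflict between Protocol Sections 5.5 and 8.3 is real and stands in current text. It permits, but does not show, an eligibility decision made after allocation at sites with unmasked staff. For that to bias the comparison, three things must hold: the exception is used with a check still open, the person deciding knows the arm, and the patients dropped differ by arm. None can be established from the documents.

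A reader might try to size the bias as excess loss in an implant arm times the IOP gap between dropped and retained patients. Assuming 2% to 5% and 3 mm Hg gives 0.02 × 3 = 0.06 to 0.05 × 3 = 0.15 mm Hg. That calculation should not be relied on:
- Neither input is in the documents.
- If 20% of patients used the exception (also an assumption), those losses would be 0.02/0.20 = 10% to 0.05/0.20 = 25% of them within a few days.
- A gap of 3 mm Hg is 3/4.0 = 0.75 of the planning SD, and the SAP model adjusts for baseline IOP and stratum, so only a residual difference would matter.
- Setting the shift against the 0.25 mm Hg planning advantage flatters it, since the planned 10 µg difference at Week 12 is 0. Against the 1.5 mm Hg margin it is 0.06/1.5 = 4% to 0.15/1.5 = 10%.
- The direction is unknown.

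The effect on power is small. Severity: minor.

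**What to change.** Delete the Baseline-visit exception from Protocol Section 8.3 so that it agrees with Section 5.5. If early contact is needed for scheduling, keep it under one of two conditions:
- every eligibility check, including any repeat laboratory result, is final and documented before IV/WRS is contacted; or
- IV/WRS may be contacted at Baseline but releases the assignment only after eligibility is confirmed on Day 1.

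In either case, add to SAP Section 7.0 a line for patients randomised but not treated, by randomised arm, with reasons and whether randomisation took place at Baseline or on Day 1. This shows whether the exception mattered and covers the Day 1 losses that the timing change cannot prevent.

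The cost is a short protocol edit, an IV/WRS setting if the second condition is chosen, one disposition line, and slightly less flexibility in scheduling administration.

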8.5 Instructions for the Patients

Patients should be instructed to strictly follow the study visit schedule and to report all changes in their condition to the investigative site.

Instruction should be given to the patient to maintain a stable dose of any concomitant medication used chronically, or any new medications initiated during the study whenever possible. Patients should be instructed to communicate any changes to their medication at their next study visit. Patients should also be reminded to contact the study site if they are experiencing any difficulties during their study participation.

Patients should keep the study medication bottles in the original kit that was provided and return the bottles to the designated (unmasked) site staff. Patients should be instructed that bottles of provided medications should only be used for 28 days each.

Patients will be instructed not to administer the study-provided eye drops the morning of study visits (except Administration Day visits) and to bring their study medications to their visit for instillation immediately after the Hour 0 IOP measurements. Site personnel and patients will be reminded to take appropriate caution during administration of study medications during the visit to ensure maintenance of masking. Patients should instill their morning dose of study-provided eye drops on the day of the Administration Day visits.

Patients should be instructed to remove their contact lenses before instillation of any topical ophthalmic medication, and to keep contact lenses out for at least 15 minutes after instillation of eye drops.

8.6 Unscheduled Visits

Additional examinations may be performed as necessary to ensure the safety and wellbeing of patients during the study period. Unscheduled visit eCRFs should be completed for each unscheduled visit. An assessment of any adverse event should be completed.

8.7 Compliance with Protocol

Patients must be able to adhere to the study visit schedule; appropriate inclusion, exclusion, and treatment criteria; permitted and prohibited medication criteria; and testing parameters as described in the protocol. At each study visit, patients will be asked if they have used their study-provided eye drops as instructed and whether they have used any concomitant medications/therapies or had any concurrent procedures since the previous visit.

Patients should be scheduled for study visits as closely to the day specified in the visit schedule as possible.

8.8 Early Discontinuation of Patients

Patients may voluntarily withdraw from the study at any time.

Patients who have received nonstudy IOP-lowering medication in only one eye will be followed for the duration of the study through the Month 20 visit.

Patients who have received nonstudy IOP-lowering medication in both eyes, or who do not complete an Administration Day visit, may discontinue the study 12 months after the last Bimatoprost SR or Sham administration at which time they should complete the Month 20/Exit visit procedures.

Notification of early patient discontinuation from the study and the reason for discontinuation will be made to the sponsor and will be clearly documented on the appropriate eCRF.

When patients exit before Month 20, the site should complete all procedures for the Month 20/Exit visit at the patient's last visit.

8.9 Withdrawal Criteria

After the first administration (or Sham), failure to undergo an Administration Day visit does not indicate total withdrawal from the study. Patients who have received nonstudy IOP-lowering medication in only one eye will continue through the duration of the study. Patients who have received nonstudy IOP-lowering medication in both eyes, or patients who do not undergo Cycle 2 or 3 (or both) Administration Visits, will still be followed for 12 months after the last Bimatoprost SR or Sham administration for safety reasons. These patients are eligible for Early Discontinuation (Early Exit) as described in Section 8.8, above.

The investigator should consider withdrawing a patient from the study early if any of the following criteria are met:

- Patient develops (or has an exacerbation of) a medical condition that, in the opinion of the investigator, compromises the patient's ability to participate in the study
- Patient develops (or has an exacerbation of) a medical condition that, in the opinion of the investigator, compromises the patient's ability to participate in the study
- Patient is unwilling or unable to continue to comply with study procedures
- Patient is unwilling or unable to continue in the study

If a patient develops (or has an exacerbation of) a medical condition that, in the opinion of the investigator, would put the patient at an unacceptable medical risk by continuing study participation, the patient will be withdrawn from the study.

Whenever possible, the decision to withdraw a patient from the study or study treatment should be discussed with Allergan.

8.10 Study Termination

The study may be stopped at his/her study site at any time by the site investigator. Allergan may stop the study (and/or the study site) for any reason with appropriate notification.

9. Adverse Events

Adverse events occurring during the study will be recorded on an adverse event eCRF. If adverse events occur, the first concern will be the safety of the study participants.

9.1 Definitions

9.1.1 Adverse Event

An adverse event is any untoward medical occurrence in a patient or clinical investigation subject administered a pharmaceutical product and that does not necessarily have a causal relationship with this treatment. An adverse event can therefore be any unfavorable and unintended sign (including an abnormal laboratory finding), symptom, or disease temporally associated with the use of a medicinal (investigational) product, whether or not related to the medicinal (investigational) product. In addition, during the screening period, adverse events will be assessed regardless of the administration of a pharmaceutical product.

Note: Adverse events must be collected once informed consent has been obtained, regardless of whether or not the patient has been administered study drug.

Progression of treatment indication including new or worsening of anticipated clinical signs or symptoms, which are collected as clinical efficacy variables and assessed as unequivocally associated with the disease progression and /or lack of efficacy, should NOT be reported as adverse events unless the disease progression is greater than anticipated in the natural course of the disease.

Adverse events will be assessed, documented, and recorded in the CRF throughout the study (ie, after informed consent has been obtained). At each visit, the investigator will begin by querying for adverse events by asking each patient a general, nondirected question such as "How have you been feeling since the last visit?" Directed questioning and examination will then be done as appropriate. All reported adverse events will be documented on the appropriate case report form.

9.1.2 Serious Adverse Event

A serious adverse event is any adverse event occurring at any dose that results in any of the following outcomes: death, a life-threatening adverse event, inpatient hospitalization or prolongation of existing hospitalization, a persistent or significant disability/incapacity, or a congenital anomaly/birth defect. Important medical events that may not result in death, be life-threatening, or require hospitalization may be considered a serious adverse event when, based upon appropriate medical judgment, they may jeopardize the patient or subject and may require medical or surgical intervention to prevent one of the outcomes listed in this definition. (See Section 9.3 for procedures for reporting a serious adverse event.)

Allergan considers all cancer adverse events as serious adverse events. In addition, Allergan considers any abortion (spontaneous or nonspontaneous) as a serious adverse event.

Preplanned surgeries or procedures for pre-existing, known medical conditions for which a patient requires hospitalization is not reportable as a serious adverse event.

Any preplanned surgery or procedure should be clearly documented in the site source documents by the medically qualified investigator at the time of the patient's entry into the study. If it has not been documented at the time of the patient's entry into the study, then it should be documented as a serious adverse event and reported to Allergan.

